## 7. Plan for surveillance of cognitive adverse effects

Cognitive adverse effects can occur because of the effect of endotoxin administration (see section 5c) and because of disrupting patient's daily routine and fatigue. Imaging studies which are common in Alzheimer's research, and often in more cognitively impaired individuals, often follow more rigorous procedures of testing. We anticipate that the latter is less likely to be a factor in the cognitive adverse effects. For our purposes we classify cognitive adverse effects as acute and chronic. We following the conventional practice of measuring global cognitive changes by monitoring functional status (ADCS-ADL in this case) and multi-domain screening instruments (MOCA in this case).

*7.1 Protocol for the monitoring of acute cognitive changes for a one-time or test-dose administration of agents*

- The patient's study partner has the PI's cell phone whom s/he can contact with any concerns
- If called, then patient screened with CAM over the phone
- If not called, then the patient is screened with CAM after 48 hours
- If intervention is required that will be prioritized
- If not, then depending on the latest possible interval for late effects there is re-screening. Otherwise Stop.
- If there is delirium, then CAM is repeated every 24 hours until resolution AND ADCS- ADL will be performed in a week to gauge the severity of the adverse effects for reporting.
- MOCA will be performed in a week regardless; and weekly using alternative versions until resolution if  $\geq$  2 change in score.

**8. Plan for Grading Cognitive Adverse Events:**

The FDA guidance does not contain guidance regarding grading of cognitive adverse effects. We use the general scheme from the FDA guidance as the starting point. Grading of cognitive function in the elderly is often based on functional abilities. This approach appears to be in harmony with the general intent of FDA's guidance.

Assessment of cognitive safety is the assessment of "the impact of clinical treatments on the ability to perceive, process, understand, and store information, make decisions and produce appropriate responses". As with many systemic adverse effects of medications the severity is often expressed in terms of functional capacity. This is particularly apt for cognition for three basic reasons:

- 1- There is no ecologically valid single indicator of "cognition" which may be accepted as reliable surrogate for the overall brain cognitive ability, say when compared to the role of ejection fraction in cardiac ischemic complications.
- 2- The most useful indicators of organ system integrity rely on measuring surrogates of broad functions of those organ system. For example, renal side effects may be detected by measuring creatinine clearance and proteinuria. It is possible and in fact in some cases

necessary to look at renal parameters in greater detail including size, filtration rate, active transport mechanism and endocrine function. Especially in patients whose creatinine is shown to be affected However, these are often unnecessary in a majority of cases. Activities of daily living may provide a similar overall surrogate for cognitive function if and only if all other factors (chiefly mobility) remain the same.

- 3- The Dementia research community defines stages of dementia in terms of their impact on activities of daily living. Several scales including the Clinical Dementia Rating are based on this idea.

#### *8.1 Protocol for stratification of acute cognitive adverse effects for reporting*

No adequate guidelines at present exist for grading of serious adverse effects of administered agents pertaining to acute cognitive changes. We will adopt the following scheme:

We use CTCAE 4.02 for guidance; DL=dependence level (see below)

Grade	Definitions	Maximal daily DL change in first week	Change of DL in 1 week
1	Mild; asymptomatic or mild symptoms; clinical or diagnostic observations only; intervention not indicated.	2	1
2	Moderate; minimal, local or noninvasive intervention indicated; limiting age-appropriate instrumental ADL*.	3	2
3	Severe or medically significant but not immediately life-threatening; hospitalization or prolongation of hospitalization indicated; disabling; limiting selfcare ADL.	4	3
4	Life-threatening consequences; urgent intervention indicated.	N/A	N/A
5	Death related to AE.	N/A	N/A

The DL is determined using a published algorithm^25:

DL	Types of Impairment	Care Needs	Scoring Algorithm versus Care Needs
0	No IADL/BADL impairment	None	No impairments in ADCS-ADL
1	Some supervision needed on isolated	Independent living with check-ins	Level 2 on any 1 item from the following clusters: Household activities, Communication and Engagement, Outside Activities

2	Supervision on multiple IADLs or loss of at least 1 Household	Limited/inf or mal home care services	Level 2 on items from at least 2 of the following clusters: Household activities, Communication and Engagement, Outside Activities, OR Level 1 on any item from the following clusters: Household activities, Communications and Engagement, Outside Activities
3	Supervision on all types of IADLs or home- bound	Extensive home care services w/ supervision	Level 2 for all items from the following clusters: Household activities, Communications and Engagement, Outside Activities, OR Level 0 on 1 item of Outside Activities, OR Level 2 for either item: Eating (Q1), Bathing (Q4)
4	Supervision on some BADLs	Assisted living + nursing	Score <2 for item Dressing (Q6B), OR Level 1 or 0 or for any items: Grooming (Q5), Bathing (Q4), OR Level 2 for item Toileting (Q3), OR Level 0 for
5	Impaired transfer OR complete incontinence	Nursing home	Level 1 for Walking (Q2), OR Level 0 for Toileting (Q3)

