### Procedure

#### Screening and selection procedures:

*Screen/Baseline visit to ADRU:* Each subject will have an initial screening visit that will include:

Screening: Demographics, history, examination, GDS, EKG, Labs, MOCA, logical memory I/II, CDR and Informed consent. Baseline: WAISIII – picture completion, digit symbol, symbol search, arithmetic, digit span, information, letter number sequencing, RAVLT, Trails A/B, Boston naming, Stroop, FAS, Rey complex figure, ADCS-ADL, CAM and NPI. In certain cases, this can take more than 4 hours and we may need to split the day into two where screening and baseline are administered on separate days.

*Possible pre-imaging visit to MRRC:* Many of the patients who will enroll will already have clinical MRI. For those who do not we will organize one for this research.

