- 48 hours after the administration of the endotoxin there will be a phone screening using CAM to check for delirium. If there is ongoing delirium then the subject will be directed to immediately go to the emergency room for evaluations and then a follow-up visit can be scheduled with the study doctor
- One week visit: RAVLT, Trail A/B, digit symbol, CAM, ADCS-ADL, MMSE/MOCA, Stroop. 1- 1.5 hrs.

*Optional additional visit for CSF draw*

In volunteers who agree to do so, one 20mls of CSF Sample 0-7days after LPS will be taken at Hospital research unit (HRU) of Yale new haven hospital and banked at [name] in [name] Laboratory. The samples will only be stored in [name] laboratory; they will not be added to one of [name] existing repositories. The samples will be used by only the investigators on this project; they will not be made available to outside researchers.

*Optional additional visits to assess Cognitive Measures with Cog-state Ipad testing*

We may obtain these measures at baseline during the week before LPS injection and the following one during the week after LPS injection. These patients will be separately consented and we will not exclude anyone if they do not accept to do these tasks.

1. Cogstate Battery (30 minutes) – This computerized test battery will assess memory and cognition. The tasks may include:
  - a. International Shopping List Task – a computerized task to assess verbal learning and memory.
  - b. Groton Maze Learning Task – a computerized task to assess executive function and spatial problem solving.
  - c. Detection Task – a computerized task to assess psychomotor function and speed of processing.
  - d. Identification Task – a computerized task to assess visual attention and vigilance.
  - e. One Card Learning Task – a computerized task to assess visual learning and memory.
  - f. One Back/Two Back Tasks – computerized tasks to assess attention and working memory

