**6 month Visits:**

The patient will have MOCA, GDS, CDR, and other neuropsych similar to screening and baseline.

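### The cognitive adverse-event grading table cannot be applied consistently: its one-week dependence-level numbers conflict with its Grade 3 wording, and its daily column has no data source

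*Combined protocol and SAP*

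**What the plan says.** All references are to the combined protocol and SAP; DSMP is its Data and Safety Monitoring Plan.

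- **Grading (DSMP 8.1).** Grades 1, 2 and 3 each have a verbal definition and two numbers. Under "Maximal daily DL change in first week" the numbers are 2, 3 and 4. For the change at one week they are 1, 2 and 3. The Grade 3 definition includes "disabling; limiting selfcare ADL"; Grade 2 speaks of instrumental ADL.
- **Dependence level (DSMP 8.1).** DL runs from 0 to 5 and is scored from ADCS-ADL items. DL 4 is labelled "Supervision on some BADLs".
- **When the ADCS-ADL is taken.** The baseline list (Section V.3, screening) ends with "Rey complex figure, ADCS-ADL, CAM and NPI". The Safety Visits text gives "48 hours after the administration of the endotoxin there will be a phone screening using CAM to check for delirium", then "One week visit: RAVLT, Trail A/B, digit symbol, CAM, ADCS-ADL, MMSE/MOCA, Stroop". DSMP 7.1 repeats the delirium screen (CAM) every 24 hours while delirium lasts, takes the ADCS-ADL at a week, and repeats the MOCA weekly if it has changed by 2 or more. For six months the text is: "The patient will have MOCA, GDS, CDR, and other neuropsych similar to screening and baseline".
- **Stopping (DSMP, stopping criteria, item x).** The study stops for one Grade 3 cognitive effect that lasts beyond a week, or for two of Grade 2 that do.

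**The concern.** Criterion x is the only stopping criterion written for cognition, and it works through the grade. If the numbers and the wording in DSMP 8.1 give different grades for the same subject, two people applying the plan in good faith can reach different stopping decisions. The subjects exposed are those who already have some functional dependence at entry, which means mainly the AD group. DSMP 5c says that the effect of endotoxin in Alzheimer's disease is unknown and names delirium as a theoretical vulnerability.

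Two further questions follow. The first is whether the daily column can be filled in at all. The second is which measurement shows that an effect has persisted.

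**Working it through.** **1. One-week numbers against the wording.** The plan gives no worked figure to reproduce, so I list the transitions. Change = DL at one week minus baseline DL. I read the tabulated numbers as minimum changes: 1 is Grade 1, 2 is Grade 2, and 3 or more is Grade 3.

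| Baseline DL | To DL 4: change, grade | To DL 5: change, grade |
|---|---|---|
| 0 | 4 − 0 = 4, Grade 3 | 5 − 0 = 5, Grade 3 |
| 1 | 4 − 1 = 3, Grade 3 | 5 − 1 = 4, Grade 3 |
| 2 | 4 − 2 = 2, **Grade 2** | 5 − 2 = 3, Grade 3 |
| 3 | 4 − 3 = 1, **Grade 1** | 5 − 3 = 2, **Grade 2** |

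If a new DL 4 or 5 is taken as a new self-care limitation, the wording gives Grade 3 in every cell. The bold cells fall below that. From DL 3 the largest possible change is 2, so numeric Grade 3 is out of reach. There is no such conflict from DL 0 or 1.

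**2. Where the line is less clean.** The scoring rule for DL 3 already admits a reduced level on eating or bathing, which are self-care items. A move from 3 to 4 may therefore not be a *new* self-care limitation. Conversely, a move from 2 to 3 through bathing would be Grade 1 by number (3 − 2 = 1) and could be Grade 3 by wording. From DL 0 to DL 3 the mismatch can run the other way: Grade 3 by number for mainly instrumental loss. The exact set of mismatches depends on which items changed.

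**3. Effect on criterion x.** Take a new DL 4 that involves a new self-care limitation and persists.

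| Baseline DL | By number | By wording |
|---|---|---|
| 0 or 1 | stop at this event | stop at this event |
| 2 | needs a second qualifying event | stop at this event |
| 3 | not counted | stop at this event |

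**4. Can subjects start at DL 2 or 3?** The AD entry criteria (MOCA of at least 17, CDR above 0, a caregiver) set no DL ceiling. DL 2 can be reached through one item: its rule includes "OR Level 1 on any item from the following clusters", naming household, communication and outside activities. DL 3 is a heavier state and looks less likely in mild disease. Baseline DL is not given.

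**5. The daily column.** DL needs the ADCS-ADL. That is scheduled at baseline and one week; in between, only the CAM is named, and the CAM does not yield a DL. A delirium that clears with DL back at baseline by day 7 has no numeric grade. Criterion x is untouched, because it requires persistence beyond a week.

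**6. Persistence.** After week 1 no ADCS-ADL is specified until month 6, about 26 − 1 = 25 weeks if six months is counted from dosing. It is not named at month 6, although a battery similar to baseline may include it. Criterion x does not say which measurement decides that an effect persists.

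**The case against.** The strongest reply is that criterion i already protects these subjects: one serious event possibly or probably related to the study stops it. The care-needs column of DSMP 8.1 places DL 4 at assisted living with nursing. Read that way, a new DL 4 is a change in level of care, which the section on worsening of Alzheimer's symptoms answers with admission (scenario 3). Under DSMP 9 an admission is serious, and persistent disability is a second route. Much of this stands. It is not complete: the care-needs column describes need rather than care received, a carer may cope at home (scenario 2), and DSMP 9 itself says that a severe grade need not make an event serious.

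On follow-up, scenario 2 requires a clinic visit within 48 hours and tracking to resolution, the endotoxin section follows subjects for a week or until symptoms resolve, and the CAM and MOCA are repeated. That also stands. What is missing is an instrument and an interval on the DL scale. The one-week ADCS-ADL can show that an effect is still present at a week, but one reading cannot show that it goes on beyond that.

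A reader might infer that the table is unusable, or that a persistent cognitive effect would go unmonitored. The documents support neither. The one-week column can be computed for every subject with the baseline and one-week ADCS-ADL, and a brief delirium can still be graded by the verbal definitions.

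**Conclusion.** The point holds as an inconsistency in a safety rule that should be fixed. For subjects starting at DL 2 or 3, the one-week numbers can place a new self-care limitation at Grade 1 or 2 while the wording places it at Grade 3. The plan does not say which governs, and criterion x depends on the answer.

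The size is bounded but not known. Somewhere between none and all of the 7 planned AD completers start at DL 2 or 3. Criterion i removes a substantial part of the consequence. The result rests on reading the numbers as minimum changes and on treating DL 4 and 5 as basic self-care limitation; the overlap at DL 3 means that a fixed count of conflicting transitions should not be claimed.

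The empty daily column is a reporting defect only. The persistence point is narrower still: the plan calls for follow-up, but does not tie criterion x to a measurement.

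**What to change.** 1. Add to DSMP 8.1 that a new basic self-care limitation attributable to the event, including any new DL 4 or 5, is Grade 3 whatever the DL-change number. The cut-offs can otherwise stay.
2. Delete the daily column, or supply it: take the ADCS-ADL by phone from the study partner at the 48-hour CAM call, and with each daily CAM repeat while the CAM is positive. The inclusion criteria require a caregiver only for AD subjects, so this applies where there is a partner.
3. If the one-week DL is above baseline, repeat the ADCS-ADL with the follow-up already planned until it returns to baseline, and judge persistence under criterion x on that.

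**Cost.** A short DSMP amendment agreed with the IRB and FDA. If the daily column is kept, there is one extra phone questionnaire per subject with a partner, and up to 4 more (days 3, 4, 5 and 6) for a subject first CAM-positive at 48 hours. Item 3 adds repeats only for subjects whose DL is still raised. The stopping rule becomes slightly more sensitive. No dose, scan or sample-size change is needed.

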## 9. Plan for Determining Seriousness of Adverse Events:

In addition to grading the adverse event, the committee will determine whether the adverse event meets the criteria for a Serious Adverse Event (SAE). An adverse event is considered serious if it results in any of the following outcomes:

1. Death;
2. A life-threatening experience in-patient hospitalization or prolongation of existing hospitalization;
3. A persistent or significant disability or incapacity;
4. Any other adverse event that, based upon appropriate medical judgment, may jeopardize the subject's health and may require medical or surgical intervention to prevent one of the other outcomes listed in this definition.

An adverse event may be graded as severe but still not meet the criteria for a Serious Adverse Event. Similarly, an adverse event may be graded as moderate but still meet the criteria for an SAE. It is important for the PI to consider the grade of the event as well as its "seriousness" when determining whether reporting to the IRB is necessary.

## 8. Stopping criteria of the study in response to Adverse Events:

Any of the following will be sufficient reason for cessation of the experiment. Items i-ix were added with the guidance of FDA:

- i. One Serious Adverse Event (SAE) that is possibly or probably study-related;
- ii. One Grade 3 bradycardia or two Grade 2 bradycardias that are considered to be possibly or probably related to endotoxin administration;
- iii. One episode of sinus pause;

- iv. One Grade 2 or 3 tachyarrhythmia (e.g., atrial, supraventricular, etc.);
- v. One Grade 3 or two Grade 2 systolic hypotension episodes that persist and require interventions, other than passive leg raising;
- vi. Death of an enrolled subject unless unequivocally not attributable to study drug (e.g., traumatic injury);
- vii. Occurrence of a life-threatening allergic/hypersensitivity reaction (anaphylaxis) requiring hemodynamic support with vasoactive medications or mechanical ventilation, the signs/symptoms of which include any of the following: bronchospasm, dyspnea, wheezing, stridor, hypoxemia, urticaria, angioedema, hives, and facial or oropharyngeal edema;
- viii. Grade 4 toxicity in a major organ system (liver, kidney, lungs, heart, etc.) in one subject; OR
- ix. Any Grade 3 toxicity in the same major organ system (liver, kidney, lungs, heart, etc.) in two subjects. Grade 3 abnormalities of multiple laboratory parameters that indicate malfunction of a single organ system (e.g., aspartate aminotransferase, alanine aminotransferase, and bilirubin for liver function; blood urea nitrogen and creatinine for renal function) in a subject will be regarded as a single toxicity for purposes of this stopping criterion.
- x. One grade 3 cognitive adverse effect which persists beyond 1 week or two grade 2 cognitive side effects which persist after a week.

## **10. Plan for expedited reporting of UPIRSOs and Serious Adverse Events to the IRB and the FDA**

The principal investigator will report the following types of events to the IRB and FDA:

Any incident, experience or outcome that meets ALL 3 of the following criteria:

1. Is unexpected (in terms of nature, specificity, severity, or frequency) given (a) the research procedures described in the protocol-related documents, such as the IRB-approved protocol and informed consent document and (b) the characteristics of the subject population being studied; AND
2. Is related or possibly related to participation in the research (*possibly related* means there is a reasonable possibility that the incident, experience, or outcome may have been caused by the procedures involved in the research); AND
3. Suggests that the research places subjects or others at greater risk of harm (including physical, psychological, economic, legal, or social harm) than was previously known or recognized.

Unanticipated Problems Involving Risks to Subjects or Others (UPIRSOs) may be medical or non-medical in nature, and include – but are not limited to – *serious, unexpected, and related adverse events* and *unanticipated adverse device effects*. **Please note** that adverse events are reportable to the IRB as UPIRSOs **only** if they meet all 3 criteria listed above.

These UPIRSOs/SAEs will be reported to the IRB in accordance with IRB Policy 710, using the appropriate forms found on the website. All related events involving risk but not meeting the *prompt* reporting requirements described in IRB Policy 710 should be reported to the IRB in

summary form at the time of continuing review. If appropriate, such summary may be a simple brief statement that events have occurred at the expected frequency and level of severity as previously documented. In lieu of a summary of external events, a current DSMB report can be submitted for research studies that are subject to oversight by a DSMB (or other monitoring entity that is monitoring the study on behalf of an industry sponsor).

**12. Plan for expedited reporting adverse events to FDA, co-investigators on the study, DSMBs, study sponsor (NIA).**

**Written reporting to FDA will be completed in a time period equal or fewer than five calendar days for all UPIRSO's and serious adverse effects.**

For the current study, the following individuals, funding, and/or regulatory agencies will be notified:

- ✓ All Co-Investigators listed on the protocol.
- ✓ Food and Drug Administration (Physician-Sponsored IND #\_\_\_\_\_)
- ✓ NIA
- ✓ Our safety committee

The principal investigator (*[name]*) will conduct a review of all adverse events upon completion of every study subject. The principal investigator will evaluate the frequency and severity of the adverse events and determine if modifications to the protocol or consent form are required.

**Statistical Considerations:** Describe the statistical analyses that support the study design.

**Primary Outcome:**

The 16 enrolled subjects will have C-PBR28 using the bolus/infusion method. Measurements will be made at baseline and 180 minutes after the injection of LPS. We will measure Total Volume of Distribution (VT) for 12 brain regions defined by MRI scan, as described (111). All primary outcomes will use the parietal ROI for calculations of both baseline activation and microglial activation reserve. For our primary outcomes we will choose the microglia activation reserve index defined as MARI = [(VT(LPS)-VT(baseline))/ VT(baseline))] X %100. In the NIMH study the greatest difference in the regional PBR28 binding between AD and cognitively normal subjects was found in the parietal lobe (7). We also found the greatest microglia activation reserve index in the parietal lobe when we applied our paradigm to young healthy controls (109). Other ROIs will be used in secondary analyses.

Statistical Considerations and Sample Size: Several comparisons of C-PBR28 VT brain level and microglia activation reserve index in the parietal lobe will be made using Student T-test to test for a difference between group means: young healthy group vs. elderly cognitively normal, as well as AD vs. elderly cognitively normal. Although this is intended as a pilot study we have performed some basic power analyses. For the comparison of baseline activation in AD vs. aged matched cognitively normal subjects based on standard deviations derived from Kreisel (7) and our own previous studies (107,109,111), using an alpha of 0.05 and power of 0.80, our study is powered to detect an effect size of > 1.6 which is not far off from the findings in the NIMH study. For the comparison of percentage post-LPS change from baseline in AD and NC groups we are powered to detect an effect size of more than 2.

